5.2 Exclusion Criteria

 Patients on antidopaminergic medications for a period of less than 1 year from date of enrollment.

PI: [name], PhD

Sponsor: UAMS

 Patients who may require adjustment of their PD medications over the 6 month period of the trial.

- History of allergic reactions to Modafinil or armodafinil.
- Uncontrolled intercurrent illness including, but not limited to, ongoing or active
 infection, symptomatic congestive heart failure, unstable angina pectoris, cardiac
 arrhythmia, mitral valve prolapse, left ventricular hypertrophy, chronic obstructive
 pulmonary disease, known malabsorption syndromes, renal disease or hepatic
 disease, or psychiatric illness/social situations that would limit compliance with study
 requirements.
- Individuals who are pregnant or breastfeeding
- Non-english speaking individuals who are unable to complete the questionnaires and other assessments in English and/or follow instructions in English.

5.3 Accrual Goal

The goal for this study is to complete 20 subjects with PD and FOG, randomized 1:1 to early start and delayed start with Modafinil. Up to 25 patients may be enrolled in order to accomplish the goal.

5.4 Recruitment Plan

Subjects will be recruited from the population of patients already performing routine gait assessments as part of an ongoing IRB by the PI ([name]; UAMS IRB # 203234). In addition subjects will be recruited from the PI's clinic patient population and from the two other movement disorders neurologists at UAMS ([name] and [name]).

6.0 INVESTIGATIONAL PRODUCT

6.1 Test Article

Modafinil

For this study Modafinil 50 mg oral capsules will be produced and dispensed by the UAMS pharmacy in gelatin capsules with microcrystalline cellulose as filler. Subjects will take Modafinil 50 mg capsule oral daily for either 12 weeks or 24 weeks depending upon whether they are in the early-start or delayed-start arm of the trial as described below (see Figure 1).

Placebo

For this study placebo capsules will be made of gelatin capsules filled with microcrystalline cellulose and will be identical to the Modafinil capsule. Subjects in the delayed start arm will receive 12 weeks of placebo followed by 12 weeks of Modafinil 50 mg oral daily (see Figure 1)

6.1.1 Dispensing

Modafinil and placebo capsules will be produced and dispensed by the pharmacy in labeled packets with appropriate instructions on how they should be taken. Both will be dispensed by the UAMS pharmacy in 6 week increments at study visits 1-4.

PI: [name], PhD

Sponsor: UAMS

6.1.2 Treatment Compliance

A pill diary will be provided to the patients in order to try and ensure compliance with the treatment regimen. Patients will also be asked to return the pill containers at each visit to help ensure compliance. If patients are unable to provide the pill diary then they will be asked to sign a form stating their compliance with the study dosing regimen.

6.2 Treatment Dosage and Administration

The research pharmacy will create a randomization log, randomizing 20 subjects 1:1 to early start or delayed start modafinil (Figure 1). Subjects will be assigned the next line in the log in order of treatment. Subjects in the early-start arm will receive Modafinil 50 mg oral daily (a.m.) for 24 weeks while subjects in the delayed-start arm will receive oral placebo for the first 12 weeks of active treatment followed by Modafinil 50 mg oral daily for weeks 13-24 of the active treatment period. The drug will be washed out for a 2 week period with repeat assessments to determine any withdrawal symptoms.

[figure not shown]

Figure 1: Delayed-start trial model with 1:1 randomization into an early-start arm with 10 subjects receiving Modafinil 50 mg oral daily for 24 weeks and 10 subjects randomized to a delayed-start arm receiving placebo for the 1st 12 weeks followed by Modafinil 50mg oral daily for weeks 13-24. Visits will be performed at initiation and randomization, followed by 6, 12, 18 and 24 week visits in the active phase with the final visit performed after a 2 week drug washout phase.

6.3 Toxicities and Dosing Delays/Dose Modifications

Any patient who receives treatment on this protocol will be evaluable for toxicity. Each patient will be assessed for the development of toxicity as described in section 9. If patients develop the following toxic side effects to Modafinil 50 mg (current FDA dosing for narcolepsy is 4 times this dose at 200 mg), they will be withdrawn from the study.

- Stevens-Johnson Syndrome
- Angioedema and Anaphylaxis
- multi-organ failure
- persistent excessive daytime sleepiness
- psychiatric symptoms (any out of mania, delusions, suicidal ideations, paranoid delusions, or auditory hallucinations)
- cardiovascular events (chest pain, palpitations, dyspnea, ischemic T-wave changes on electrocardiogram)

PI: [name], PhD

Sponsor: UAMS

Missed doses will be tabulated using a pill diary and if more than 14 days of dosing was missed in either the first 12 weeks or the second 12 weeks of the active treatment phase then this would warrant removal of the patient from the study.

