6.6 Duration of Therapy

In the absence of treatment delays due to adverse events, treatment may continue for a total of 24 weeks or until:

- Disease progression is documented per the judgment of the investigator
- Inter-current illness that prevents further administration of treatment
- Unacceptable adverse event(s) (see section 6.3)
- Patient decides to withdraw from the study, OR
- General or specific changes in the patient's condition render the patient unacceptable for further treatment in the judgment of the investigator.

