6.8 Removal of Patients from Protocol Therapy

Patients will be removed from therapy when any of the criteria listed in Section 7.4 apply. Notify the Principal Investigator, and document the reason for study removal and the date the patient was removed in the Case Report Form. The patient should be followed-up per protocol.

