7.4 Removal of Subjects from Study

Patients can be taken off the study treatment and/or study at any time at their own request, or they may be withdrawn at the discretion of the investigator for safety, behavioral or administrative reasons. The reason(s) for discontinuation will be documented and may include:

- Patient voluntarily withdraws from treatment (follow-up permitted);
- Patient withdraws consent (termination of treatment and follow-up);
- Patient is unable to comply with protocol requirements;
- Patient demonstrates disease progression (unless continued treatment with study drug is deemed appropriate at the discretion of the investigator);
- Patient experiences toxicity that makes continuation in the protocol unsafe;
- Treating physician judges continuation on the study would not be in the patient's best interest:
- Patient becomes pregnant (pregnancy to be reported along same timelines as a serious adverse event);
- Lost to follow-up. If a research subject cannot be contacted despite repeated attempts during the 6 month period they will be considered lost to follow-up. All attempts to contact the subject during the 6 months must be documented and approved by the Data Monitoring Committee.

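### Withdrawal from the study under section 6.3 can cost the week-12 FOG-Q, section 6.8 leaves open whether it should, and the 6-week inclusion rule ties the analysis to time on study

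*Combined protocol and SAP*

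**What the plan says.** **Leaving.**
- Section 6.3: patients with any of the listed toxicities "they will be withdrawn from the study". If more than 14 dosing days are missed in either 12-week half, "then this would warrant removal of the patient from the study".
- Section 6.8: "Patients will be removed from therapy when any of the criteria listed in Section 7.4 apply". It then says: "The patient should be followed-up per protocol".
- Section 7.4 lists, among its reasons, "Patient experiences toxicity that makes continuation in the protocol unsafe" and "Patient is unable to comply with protocol requirements". Its opening sentence covers removal from treatment, from the study, or from both. Follow-up is expressly ended for one reason only: "Patient withdraws consent (termination of treatment and follow-up".
- Section 6.7, headed as the duration of follow-up, describes a single visit two weeks after treatment ends, to look for withdrawal effects.

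**Measuring.** The section 7.3 table schedules the FOG-Q at screening and at weeks 6, 12, 18, 24 and 26.

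**Analysing.**
- Section 4.4.1.1 includes in the week-12 FOG-Q comparison those who drop out after at least 6 weeks. The same sentence appears under 4.4.2.1, 4.4.2.3, 4.4.2.4 and 4.4.3.1.
- Section 6.9 allows a patient with less than 2 weeks of treatment to be replaced in the same arm. It does not say whether the replaced patient is analysed.
- Section 10 names a two-group repeated-measures linear model. It defines no analysis set and no handling of missing scores.

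**The concern.** Sections 6.3 and 6.8 can be applied to the same event with different results. A patient with a listed toxicity leaves the study under 6.3. The same patient also meets a 7.4 criterion, and under 6.8 comes off therapy and is followed. Site staff cannot tell from the text whether to collect the next FOG-Q.

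The toxicities in 6.3 are those attributed to modafinil, and in weeks 0 to 12 only the early-start arm takes it. If 6.3 prevails, primary outcomes may therefore go missing for reasons linked to treatment, in the one period that compares drug with placebo. The inclusion sentence in 4.4 then makes membership of the analysis depend on something that happens after randomisation. Either could make modafinil look better or worse than it is.

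**Working it through.** **1. The plan's own figure.** Section 10 states more than 80% power within an arm for a 1.75 SD difference among six time-point means with 10 patients. By noncentral F, with noncentrality 10 × 1.75² / 2 = 15.31, power is 83.4%, so the figure reproduces. It is not in dispute here. For scale, 9 patients give 78.0% and 8 give 71.5%.

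**2. What is lost if 6.3 is applied as written** (six FOG-Q visits, section 7.3):

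| Patient leaves | Scores lost | Week-12 score |
|---|---|---|
| before week 6 | 5 of 6 | none; baseline only |
| at the week-6 visit, once scored | 4 of 6 | none |
| at the week-12 visit, once scored | 3 of 6 | present |

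**3. The two routes out.** Toxicity can occur at any time. Missed doses would mostly come to light at visits, when containers are returned (section 6.1.2). To be found at week 6, a patient must have missed at least 15 of 42 doses (15/42 = 36%). Anyone who crosses the threshold later is found at the week-12 visit, where the FOG-Q is due anyway. The toxicity route is the one that matters for week 12.

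**4. The time windows.** Below 2 weeks a patient may be replaced (6.9). From 6 weeks a dropout is included (4.4). Between 2 and 6 weeks, which is 28 of the 84 placebo-controlled days (33%), a patient is neither replaceable nor, by implication, analysed.

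**5. What follows without assumptions.** Each patient is 1/10 of an arm. The FOG-Q runs from 0 to 24 (section 8.1.1), so k missing week-12 scores leave that arm's mean undetermined over 24k/10 points: 2.4 for one and 4.8 for two. This is an outer bound, not an estimate of bias.

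**6. Illustration on assumed losses.**
- Suppose that k = 1 or 2 of 10 are lost from one arm and none from the other, and that their change differs from the rest by 0.5 to 1 SD.
- SD of change = 3.58 × √(2(1 − ρ)), which is 3.58 at ρ = 0.5 and 2.77 at ρ = 0.7. Both values of ρ are assumed; 3.58 is the SD in section 10.
- Shift = (k/10) × (0.5 to 1 SD) = 0.05 to 0.20 SD. In points, that is 0.05 × 2.77 = 0.14 up to 0.20 × 3.58 = 0.72, in either direction.
- Standard error at 10 v 10 = √(2/10) = 0.447 SD, so the shift is 0.11 to 0.45 standard errors.
- Rejection rate of a two-sided 5% test with no true effect, by noncentral t: 5.1% (k = 1, 0.5 SD), 5.5% (k = 1, 1 SD), 5.5% (k = 2, 0.5 SD) and 6.8% (k = 2, 1 SD).
- Equal losses of similar patients in both arms would cancel.

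**7. What a likelihood model can recover without further visits.** A patient with a baseline score only gives the model nothing after baseline to work from, so the shift stays almost as it was. A patient with a week-6 score does help. If week-6 deviations carry over to week 12 with an assumed slope of 0.7, and the patient deviates equally at both visits, a shift of 0.20 SD falls to (1 − 0.7) × 0.20 = 0.06 SD.

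**The case against.** Several stronger readings are tempting, and the documents do not support them.

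- *That 6.8 with 7.4 plainly keeps these patients in the FOG-Q schedule.* Section 6.7, just before 6.8, describes follow-up as one post-treatment visit, and 7.4 allows removal from the study itself. The instruction in 6.8 can mean that visit alone. This stands: the text is ambiguous, and on the narrow reading continued FOG-Q collection would be a new requirement. The missing week-12 scores remain on either reading.
- *That 6.6 and 9.7 contradict 6.3.* Section 6.6 ends treatment for "Unacceptable adverse event(s) (see section 6.3"), and 9.7 lets dosing stop for the same cause. A patient who leaves the study also stops treatment, so both fit either reading.
- *That early dropouts are expressly excluded.* They are not; exclusion is only implied. The 6-week mark is also the first FOG-Q after baseline, so under the present visits leaving these patients out adds little to the loss already caused by the missing scores.
- *That same-arm replacement biases the comparison, or that the 20-line log is faulty.* A replacement who inherits a randomly assigned slot is not in itself a bias, and a 20-line log is consistent with 6.9.
- *That the bias is known to be material.* The losses in the illustration are assumed and one-sided. The adverse-event table in section 9.1.4, as far as it can be read, gives palpitation 2% v 1%, somnolence 2% v 1% and chest pain about 3% v 1%. The excesses sum to about 4 percentage points, or 0.4 of a patient in 10. Section 6.3 puts the trial dose at a quarter of the narcolepsy dose. The largest illustrated shift is 0.72/6.265 = 11% of the difference in section 10.

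This is also a pilot whose stated goal is to estimate means. That limits the weight of the point. It does not tell staff whether to collect the score.

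**Conclusion.** The point holds, as something that should be fixed rather than a fatal flaw. Three things rest on the text alone: 6.3 and 6.8 leave unsettled whether a patient who stops for toxicity keeps the scheduled FOG-Q visits; following 6.3 removes the week-12 score of anyone withdrawn before that visit; and the inclusion sentence in 4.4 conditions on time on study after randomisation.

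Confidence is high on the wording and low on the consequence. Whether any patient will be lost this way, from which arm, and in which direction the estimate would move cannot be known from the documents. The range of 0.14 to 0.72 points is an illustration and should not be read as a forecast.

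**What to change.** Leave the rules on who stops treatment unchanged.

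**(a) Collection.** Reconcile 6.3, 6.7, 6.8 and 7.4 so that stopping study drug does not in itself end the outcome assessments already scheduled, at least the FOG-Q at weeks 6 and 12. The exceptions are withdrawal of consent and any assessment that the investigator judges unsafe.

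**(b) Analysis.** Together with (a), replace the 6-week sentence wherever it appears in 4.4. All randomised patients, including any replaced under 6.9, are analysed in their randomised arm, with all available data in the planned repeated-measures model fitted by likelihood. Add an on-drug sensitivity analysis. On its own, (b) can reduce bias for patients with a week-6 score but does little for those with baseline only, so the two belong together.

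Same-arm replacement and the 20-line log need not change.

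**Cost.** Protocol wording and a few scheduled visits off drug. The FOG-Q takes 2 to 3 minutes (section 7.2). Off-drug scores will dilute the effect somewhat, which the sensitivity analysis will show. The arms may be slightly unequal if replaced patients are kept. Stride length will still be missing where gait testing is omitted. The wording should be settled before patients leave, because scores not collected cannot be recovered.

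### Section 6.3 takes subjects out of the study for toxicity or missed doses, while 6.8 keeps those removed from therapy in follow-up; the effect is small and the wording is cheap to fix.

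*Combined protocol and SAP*

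**What the plan says.** Section 6.3 contains two exit rules.

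- **Toxicity.** Subjects with any listed toxicity "they will be withdrawn from the study". The list includes "persistent excessive daytime sleepiness".
- **Missed doses.** The pill diary is counted, and "if more than 14 days of dosing was missed in either the first 12 weeks or the second 12 weeks" of active treatment, "this would warrant removal of the patient from the study".

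Section 6.8 reads differently: "Patients will be removed from therapy when any of the criteria listed in Section 7.4 apply". It then adds: "The patient should be followed-up per protocol". Section 7.4 names toxicity among its criteria. It allows removal from treatment, from the study, or both, and does not say which applies to toxicity. Withdrawal of consent is the only exit by choice that 7.4 says ends follow-up.

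Sections 6.6 and 9.7 both refer back to 6.3, but only as a reason to end treatment or dosing.

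Epworth is a secondary endpoint at 12 weeks (4.4.2.4). Subjects who drop out after at least 6 weeks are included, but the text does not say which value stands in for week 12. The first scheduled post-baseline visit is at week 6, and the schedule in 7.3 has no early-termination visit. Section 6.9 allows replacement only below 2 weeks of treatment. Section 10 plans a two-group repeated-measures linear model and states no method for missing data.

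**The concern.** Staff who see a listed toxicity have two instructions that do not fit together: end participation (6.3), or stop the drug and keep the visits (6.8). Under the first, outcome data after that point are lost for a reason tied to treatment, on every endpoint. The adverse-event follow-up that 4.4.2.2 describes is lost with them. The missed-dose rule, read literally, does the same for poor adherence.

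Epworth shows the problem most directly. A subject withdrawn for sleepiness before week 12 has no week-12 Epworth, so whether the value is missing depends on the quantity being measured. A subject withdrawn between weeks 2 and 6 is worse placed: no post-baseline Epworth, outside the six-week inclusion rule, and not replaceable under 6.9. A true difference between arms in either direction would then tend to shrink, because the arm with more sleepiness loses more of its sleepy subjects.

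Stopping the drug for these events is a safety judgement and is not questioned here.

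**Working it through.** The plan gives no figure for withdrawals or for Epworth variability, so there is nothing of its own to reproduce on this point.

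**1. Which sections bear on follow-up**

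| Section | What ends | What it says about visits |
|---|---|---|
| 6.3, toxicity | Participation in the study | None, if literal |
| 6.3, missed doses | Participation (warranted, not mandatory) | None, if literal |
| 6.6 | Treatment | Silent |
| 6.8 | Therapy | Follow-up continues |
| 7.4 | Treatment and/or study | Not settled for toxicity |
| 9.7 | Dosing, at the investigator's discretion | Silent |

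Only 6.8 gives an instruction that opposes 6.3.

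**2. How often sleepiness could trigger withdrawal**

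The only rates in the documents are somnolence 2% on modafinil and 1% on placebo (Section 9.1.4), from other populations. With 10 per arm:

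- Any case: 1 − 0.98^10 × 0.99^10 = 0.261, so 0.739 for none.
- A case before week 6, assuming half start by then: 1 − 0.99^10 × 0.995^10 = 0.140.
- Assumed 1% in both arms: 1 − 0.99^20 = 0.182; before week 6, 1 − 0.995^20 = 0.095.
- Assumed 5% in both arms: 1 − 0.95^20 = 0.642; before week 6, 1 − 0.975^20 = 0.397.

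The trigger is narrower than any somnolence, and the rate in Parkinson's disease is not given.

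**3. Average effect on the week-12 Epworth difference (assumed model)**

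Work in SD units of a single Epworth value. A subject is stopped when the change from baseline to an unobserved week-3 value exceeds a threshold c, set to give a chosen stop rate on placebo. Stopped subjects are excluded. Let δ be the true effect, s3 and s12 the SDs of change at weeks 3 and 12, k their covariance, and λ(a) = φ(a)/Φ(a). Then

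estimate = δ − (k/s3) × [λ((c − δ)/s3) − λ(c/s3)], and SE = s12 × √(2/10).

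Two correlation patterns were used: 0.7 between all times (SE 0.346), and 0.7 per 6 weeks, autoregressive (SE 0.452).

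Example with equal correlation, 0.5% placebo stops and δ = +0.30 (a harm):

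- s3 = s12 = √0.6 = 0.775 and k = 0.3.
- c = 2.576 × 0.775 = 1.995, and (c − δ)/s3 = 2.188.
- λ(2.188) = 0.0370 and λ(2.576) = 0.0145.
- Loss = (0.3/0.775) × 0.0224 = 0.0087 SD, which is 0.0087/0.346 = 2.5% of one SE.

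Over both patterns:

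| Placebo stops before week 6 | True benefit of 0.3 or 0.5 SD: loss | True harm of 0.3 SD: loss |
|---|---|---|
| 0.5% (half of 1%) | 1.1% to 1.4% of one SE | 2.5% to 3.5% of one SE |
| 1% to 2% | 0.006 to 0.020 SD; 1.9% to 4.4% of one SE | 0.014 to 0.038 SD; 4.0% to 8.3% of one SE |

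With δ = 0 the loss is zero. The 0.5% row matches the rates in step 2. The 1% to 2% row is a high range: in the harm case it implies early stops on modafinil of 2.6% to 6.3%, above the 2% total in Section 9.1.4.

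**4. What keeping visits would recover**

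Assume stopped subjects attend week 12 with the drug effect gone. At placebo stop rates of 1% to 2%, a true benefit of 0.30 is then estimated at 0.298 to 0.299 and a true harm of 0.30 at 0.281 to 0.292. That recovers at least 80% of the loss for a benefit and about 33% to 57% for a harm.

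**The case against.** The strongest reply is that the protocol uses its terms loosely and already contains the right answer. Section 7.4 is titled as removal from the study, yet 6.8 uses the same list for removal from therapy and then asks for follow-up. A site may well keep the visits, so loss is possible but not certain. That stands.

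Two features of the plan also soften the effect. A repeated-measures model can use week-6 values for subjects who leave later, and 4.4.2.4 keeps those subjects in. Section 6.9 allows replacement of subjects lost before 2 weeks. Both points stand, but neither helps a subject withdrawn between weeks 2 and 6.

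A reader might infer three stronger things that the documents do not support.

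- **That 6.3 also contradicts 6.6 and 9.7.** Ending treatment or dosing is compatible with leaving the study, and neither section speaks about visits.
- **That the missed-dose rule would remove most subjects stopped for toxicity even if the toxicity sentence were corrected.** In an 84-day period a last dose on or before day 69 leaves at least 84 − 69 = 15 days without drug. This holds only if days after an ordered stop count as missed. The rule is tied to the pill diary, reads as a compliance rule, and says removal is warranted rather than required.
- **That Epworth would be materially biased.** Losing the single sleepiest of 10 subjects in one arm only would shift that arm's mean by about 0.17 SD, but the documents give no reason to expect such a one-sided loss. The label rates make no case at all the likelier result.

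**Conclusion.** The point holds as a minor one. Section 6.3 takes subjects out of the study where 6.8 would keep those with toxicity in follow-up. Read literally, its two rules lose later data for reasons tied to tolerability or adherence, on all endpoints. The case rests on that wording and on how cheaply it can be put right, not on a large bias.

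For Epworth the average loss is about 1% to 4% of one standard error at the early stop rate that the label figures imply, and 2% to 8% at rates two to four times higher. It could not plausibly change a conclusion about a secondary endpoint in a 20-subject pilot. These sizes rest on assumed rates, timing, correlations and effect sizes, and on excluding early withdrawals.

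**What to change.** - In 6.3, replace withdrawal from the study with: *withdrawn from study drug and followed at scheduled visits as far as clinically able, with at least the questionnaires and the adverse-event assessment*. This agrees with 6.8. It does not require the full walkway battery after events such as Stevens-Johnson syndrome or multi-organ failure.
- State that the 14-missed-days rule ends study drug, not visits. This also settles whether days after an ordered stop matter.
- In the endpoint definitions and Section 10, include every randomised subject with any post-baseline value in the repeated-measures analysis. Report discontinuations by arm and reason. This replaces the six-week inclusion rule, so it is an analysis decision as well as a wording change.

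The cost is a few sentences and a few extra visits for few subjects. The limit is that week-12 values taken off drug only partly recover a drug-caused increase in sleepiness, which is why the report by arm and reason is needed.
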